5.2 Exclusion Criteria

An individual who meets any of the following criteria will be excluded from participation in this study:

1. Disorder other than PPA known to cause language dysfunction
2. Diagnosis of nonfluent/agrammatic subtype of primary progressive aphasia
3. History of traumatic brain injury
4. Uncontrolled seizure disorder and/or recent (< 5 years) history of seizure
5. Metal implants in the head or neck
6. Any skin disorder or skin sensitive area near stimulation locations
7. Pregnant or breastfeeding. Given the age range of our potential participants, we do not anticipate excluding anyone on the basis of pregnancy or breastfeeding. While there are no known or theoretical safety risks of tDCS in this special population, we routinely have included this eligibility in all our tDCS studies to date out of an abundance of caution. Further, in reference to our outcomes for this study, pregnancy and/or breastfeeding status may have unique cognitive features secondary to the influence of hormones. Participants should not become pregnant while participating in this study. If they are able to become pregnant, they will be required to use a medically-accepted method of birth control while they participate in the study:
 - Hormonal methods like birth control pills, patches, vaginal rings or implants
 - Barrier methods such as condoms or a diaphragm used with spermicide (a foam, cream or gel that kills sperm)
 - Intrauterine device (IUD)
 - Abstinence (no sex)

Exclusion criteria may be confirmed through medical records, screening assessments and self-report.

5.3 Vulnerable Subjects

We will enroll PPA patients early in the disease course and with language loss as their primary impairment. To ensure the ability to meaningfully participate, consistent with all of our RS-tDCS protocols, we will screen to include participants with premorbid intellectual functioning in at least the average range, and screen to exclude those participants with severely impaired current level of cognitive functioning. Consistent with our RS-tDCS protocol, premorbid cognitive impairment will be estimated using the verbal Wide Range Achievement Test-4th edition (WRAT-IV) or the nonverbal Peabody Picture Vocabulary Test-4th edition (PPVT-4) as a proxy of expressive vocabulary, which is an established method to estimate premorbid cognitive ability. A cut off of 1.5 SD below age normative means will be used for exclusion criteria. Current level of cognitive functioning will be estimated using the nonverbal Matrix Reasoning subtest from the Wechsler Adult Intelligence Scale-4th Edition (WAIS-IV) that measures abstract reasoning. A cut-off of 3 SD below age normative means (indicating greater than moderate impairment) will be used for exclusion criteria.

5.4 Strategies for Recruitment and Retention

Potential subjects who meet the eligibility requirements as determined by the inclusion and exclusion criteria will be contacted by a trained member of the study team. Diagnosis of PPA and tDCS eligibility will be confirmed by medical record review and a signed tDCS safety form sent to study staff prior to study enrollment.

A patient who is seeing one of these medical staff members as their treating clinician will be introduced to the study by that medical staff member. If the patient is interested and agrees to be contacted, a team member will contact them on the phone (or in-person if participant is already in clinic) using an IRB-approved phone script to provide additional study information and pre-screen to assess eligibility. Verbal responses will be recorded on a separate pre-screen verbal checklist. For any subject who is ineligible, or who is eligible but decides not to participate, we will immediately destroy the data collected during the pre-screen.

An IRB approved flyer will be posted in local physician offices and waiting rooms and throughout NYU and support organizations. In addition to recruitment at NYU, we will post these flyers around the Ambulatory Care Center (ACC) for patients to recruit from the entirety of the Neurology department and from any number of people who come to visit the ACC on [name] or have an appointment at [name].

An IRB approved study description will be posted on PPA related websites and shared with appropriate list-services related to those websites.

Diagnosis of PPA will be confirmed by patient medical records. Non-NYU patients will be asked to submit their medical records for confirmation. All patients will complete a tDCS safety questionnaire to confirm eligibility for tDCS administration (e.g. no metal in head or neck, history of epilepsy, etc.)

A description of the study including objectives and the expectations of the subject's participation will be explained. Potential participants will be clearly informed that they have the right not to participate in the study and that declining participation will not in any way affect their clinical care at NYU Langone Health. Subjects will additionally verbally confirm if they meet eligibility criteria.

Consent and assent of study participants will take place in a private telecommunication room (Zoom).

Recruitment procedures will be conducted in private patient rooms during direct subject encounters with their healthcare provider. Any identifiable data that is collected during recruitment will be kept in a locked filing cabinet in a locked office. Any identifiable data from screening failures will be destroyed immediately after the recruitment period has ended. If a subject requests information regarding opting out of further recruitment for all research, subjects will be directed to contact study coordinator or have subjects contact [contact] or [name].

5.1 Informed Consent Process

Consent forms describing in detail the study device, study procedures, and risks are given to the participant and written documentation of informed consent is required prior to starting intervention / administering study product. The following consent materials are submitted with this protocol: informed consent form.

5.1.1 Consent Procedures and Documentation

Informed consent is a process that is initiated prior to the individual's agreeing to participate in the study and continues throughout the individual's study participation. Extensive discussion of risks and possible benefits of participation will be provided to the participants and their families. Consent forms will be IRB-approved and the participant will be asked to read and review the document. The investigator will explain the research study to the participant and answer any questions that may arise. All participants will receive a verbal explanation in terms suited to their comprehension of the purposes, procedures, and potential risks of the study and of their rights as research participants. Participants will have the opportunity to carefully review the written consent form and ask questions prior to signing. The participants should have the opportunity to discuss the study with their relatives or think about it prior to agreeing to participate. The participant will sign the informed consent document prior to any procedures being done specifically for the study. The participants may withdraw consent at any time throughout the course of the trial. A copy of the signed informed consent document will be given to the participants for their records. The rights and welfare of the participants will be protected by emphasizing to them that the quality of their medical care will not be adversely affected if they decline to participate in this study.

Subjects may be mailed an informed consent form and a link to the Zoom room to meet in after they have reviewed the consent. The study team member will then explain the consent to the subject, and ask if the subject has any

questions. If the subject agrees to participate, they will sign the informed consent document and mail it back to the study team via a provided return label. Alternatively, the consent form may be sent via email by a study team member for the participant to print, sign, and return via SendSafe. The consent process, including the name of the individual obtaining consent, will be thoroughly documented in the subject's research record.

Capacity to Consent

Subject capacity to provide informed consent will be determined by trained team members or PI who will ask the participant open-ended questions regarding their understanding of key research information. All team members will be trained in GCP-ICH guidelines and will receive additional training by the PI or an experienced study team member. Global cognition will be assessed using resources accommodated for individuals with language impairment (WRAT-IV or PPVT-4, WAIS-IV Matrix Reasoning). These measures will be given prior to study enrollment with scores greater than 3.0 SD's below age-normative scores being a cut-off for study inclusion.

The results of the capacity assessment (WRAT-IV or PPVT-4, and WAIS-IV Matrix Reasoning) will not be placed in the subject's medical record. This information will only be used for research purposes and will not be considered clinical data.

Prospective subjects will be informed of the results of the capacity assessment after it's conducted. If an individual is found not to have the capacity to consent, the assessor will explain this to the individual. The assessor will provide the necessary resources and referrals for further care and evaluation.

Ongoing Assessment of Capacity

At each study visit, subjects will have direct interaction with the licensed clinicians referenced above. If the licensed clinicians have any concerns about the subject's capacity, a formal capacity assessment will be conducted as described above.

Over the course of the study, it is possible that a subject who had capacity at enrollment may lose capacity or capacity may fluctuate. Subjects who lose capacity will be withdrawn. Subjects who appear to be unduly distressed will be withdrawn from the research in a manner consistent with good clinical practice.

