5.1 Inclusion Criteria

In order to be eligible to participate in this study, an individual must meet all of the following criteria:

1. Ages 45-85 (inclusive)
2. Primary progressive aphasia diagnosis (logopenic or semantic variant)
3. Wide Range Achievement Test (WRAT) score < -1.5 SD, serving as a literacy proxy for premorbid cognitive ability and ensuring English language fluency sufficient for participation in the study procedures. If participants are not fluent enough to perform this task, the Peabody Picture Vocabulary Test (PPVT) will instead be administered with the same cut-off score of < -1.5 SD.
4. WAIS-IV Matrix Reasoning T score < 20 , serving as an index of current general cognitive functioning to exclude those with severe cognitive impairment
5. Stable and continuous access to internet service, email (WiFi "hotspot" to be provided if needed)
6. Fluent in English language (due to outcomes validated in English versions only)

Inclusion criteria may be confirmed through medical records, screening assessments and self-report.

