5.2 Duration of Study Participation

Study participation will last approximately 1 month and will include:

- Remote consent (20 minutes), with participant provided as much time as they need to review consent form. Once consented, participant will be scheduled for telehealth research screening. The screening will be scheduled based on participant and study/physician availability, which can occur on the same day as consent and anticipated to be within one week of consent.
- Baseline speech and language assessment & tDCS Session 1 (approximately 3 hours: 20 minutes to orient to device, 1.5 hour assessments, 30 minute tDCS session, 15 additional minutes of word naming practice).
- tDCS treatment sessions (20 x 30 min session over 4 weeks)
- tDCS Session 20 & Treatment-end (2 hours)

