5.3 Total Number of Participants and Sites

Recruitment will end when approximately 30 participants are enrolled (sign consent) through NYU Langone Health, Department of Neurology.

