8.3.2 Consent & Telehealth medical screening

- Remote consent through SendSafe (20 minutes)
Once consented, study personnel will send tDCS and study materials to participant

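### The WRAT/PPVT and Matrix Reasoning tests must precede enrolment, but enrolment means signing consent and nothing may be done before signing; no visit lists the tests, and three sections give different WRAT/PPVT limits

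*Combined protocol and SAP*

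**What the plan says.** Several section numbers in chapter 5 occur twice, so headings are given here.

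**Timing of the tests.** Under Capacity to Consent (section 5.1.1), on the WRAT-IV or PPVT-4 and WAIS-IV Matrix Reasoning: "These measures will be given prior to study enrollment". The same text labels them as the capacity measure: "The results of the capacity assessment (WRAT-IV or PPVT-4, and WAIS-IV Matrix Reasoning". It adds that the results stay out of the medical record and serve research only. It opens, however, by saying that capacity is determined through open-ended questions on the participant's understanding.

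**Consent rule.** Section 5.1.1: "The participant will sign the informed consent document prior to any procedures being done specifically for the study".

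**Meaning of enrolment.** Total Number of Participants and Sites: "Recruitment will end when approximately 30 participants are enrolled (sign consent".

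**Screening visit.** Duration of Study Participation: "Once consented, participant will be scheduled for telehealth research screening". It may be held on the day of consent and is expected within a week. Section 4.1 also mentions a consent/research screening visit. Neither place lists its content.

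**Equipment.** Section 8.3.2, headed as consent and telehealth medical screening, lists remote consent and then: "Once consented, study personnel will send tDCS and study materials to participant".

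**WRAT/PPVT limit.** Vulnerable Subjects: "A cut off of 1.5 SD below age normative means will be used for exclusion criteria". Capacity to Consent applies 3.0 SD to all the tests. Inclusion Criteria, item 3, requires: "Wide Range Achievement Test (WRAT) score < -1.5 SD", with the same limit for the PPVT.

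**The concern.** The tests do two jobs: they are inclusion criteria, and the protocol also calls them its capacity assessment, in people with progressive language impairment. Their place relative to the signature therefore matters for consent as well as for eligibility. As written, staff must break either the rule on when the tests are given or the rule on what may precede the signature. Someone working only from sections 8 and 19 finds no instruction to give the tests.

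The statistical stake is the enrolled group and its denominator. The primary outcome is the percentage of participants completing at least 16 of 20 sessions. Recruitment stops at about 30 signatures. If the tests follow consent, a person who fails them has already used a place, and section 10 defines no analysis set that says whether that person counts. The conflicting limits add a second uncertainty, since the same score can lead to opposite decisions.

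**Working it through.** The plan gives no figure on this point to reproduce. The check sets the sections side by side and adds one small calculation.

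**1. Order of events.** Let T be the time of the tests, E enrolment and S the signature.

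- Capacity to Consent: T before E.
- Total Number of Participants and Sites: E = S.
- Section 5.1.1: S before any study-specific procedure. The tests are study-specific, since their results are for research only. So S before T.

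The first two give T before S; the third gives S before T. They cannot all hold. Relaxing any one of them removes the conflict.

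**2. Where the tests are scheduled.**

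| Place | What it lists | WRAT, PPVT or Matrix Reasoning? |
|---|---|---|
| 8.1 Study Procedures | records check, training, tolerability test, questionnaires, word list, QAB, BNT, COWAT, sessions | no |
| 8.2 Study Assessments | self-report scales, trained and untrained words, QAB, BNT, COWAT | no |
| 8.3.1 Pre-Screening | phone screen, records, safety questionnaire, then baseline scheduled | no |
| 8.3.2 Consent and screening | remote consent, shipment | no |
| 8.3.3 to 8.3.6 | language assessment, questionnaires, device training, sessions, equipment return | no |
| 19 Schedule of Events, Screening column, visible rows | medical history, written consent | no |

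The tests appear only in Inclusion Criteria, Vulnerable Subjects and Capacity to Consent. The open-ended understanding questions have no entry in sections 8 or 19 either.

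**3. WRAT/PPVT limit, each section read literally.**

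| Score relative to the norm | Vulnerable Subjects (1.5 SD) | Capacity to Consent (3.0 SD) | Inclusion Criteria (below -1.5 SD required) |
|---|---|---|---|
| above -1.5 SD | eligible | eligible | not eligible |
| between -1.5 and -3.0 SD | excluded | eligible | eligible |
| below -3.0 SD | excluded | excluded | eligible |

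No row agrees across the three sections. If the direction in Inclusion Criteria is a slip, the conflict is confined to the middle row. For Matrix Reasoning, Vulnerable Subjects and Capacity to Consent agree on 3 SD, but inclusion criterion 4 (a T score under 20) is worded in the same reversed direction although its stated purpose is to exclude severe impairment.

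**4. Compliance denominator.** Suppose 30 people sign, k of them fail the tests afterwards, and all 30 stay in the denominator. The highest attainable compliance is (30 - k)/30. The value of k is not in the documents; as an assumed range:

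- k = 0: 30/30 = 100%
- k = 1: 29/30 = 96.7%
- k = 3: 27/30 = 90.0%

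Each failure costs 1/30 = 3.3 percentage points. If failures are dropped instead, the estimate rests on 30 - k people. The plan does not say which applies.

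**The case against.** **The contradiction hangs on one parenthesis.** The words on signing consent say how a recruitment stop is counted and do not stand in a definitions section. Enrolment may have been meant loosely in the capacity text. Consent followed by research screening is a workable order, and Inclusion Criteria allow confirmation by screening assessments. This is a fair reading of the likely intent and it points to the fix. But the parenthesis is the only gloss on enrolment in the document, and the capacity text calls those tested prospective subjects, which fits testing before signature. The Informed Consent Process section has a weaker rule (consent before the intervention starts), but section 5.1.1 is stricter and governs study procedures.

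**Capacity could go unchecked.** A reader might infer this from the tests being labelled the capacity assessment while having no visit. The documents do not support it. The stated method for determining capacity is open-ended questioning, and a formal assessment follows if clinicians have concerns at any visit.

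**Stimulators go out before eligibility is known.** A reader might infer this from section 8.3.2. That section says only that shipment follows consent; it does not place shipment before screening. Diagnosis and tDCS safety eligibility are checked earlier, and the device cannot run without a one-time code from the technician. At most, the cognitive criteria are open when equipment is sent.

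**The two limits differ about 50-fold.** On normal norms, 1.5 SD removes Φ(-1.5) = 6.7% and 3.0 SD removes Φ(-3.0) = 0.13%, a ratio of about 49. That describes a reference population. The score distribution of PPA patients is not given, so the ratio says nothing about how many participants are affected.

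**One site, run by the authoring team.** It is true that this team would probably give the tests, since criteria 3 and 4 cannot be confirmed otherwise. That lowers the practical risk but does not settle the order or the limit.

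**Conclusion.** The point holds as a conflict of rules and a gap in the schedule. The three timing rules are incompatible, the tests that decide criteria 3 and 4 have no listed visit, and the WRAT/PPVT limit differs in size and direction across three sections. Every participant passes through this step. The number whose eligibility would change cannot be derived from the documents. The effect on the primary outcome is 3.3 points off the highest attainable compliance per test failure, on the assumptions that failures occur after signature, count among exactly 30 and stay in the denominator.

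The documents do not show that people will be tested without consent or treated without a capacity check. The passages should be reconciled before recruitment; nothing here undermines the design itself.

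**What to change.** 1. Reconcile the timing rules in section 5.1.1 with Total Number of Participants and Sites: understanding questions before the signature, then the signature, then the WRAT-IV or PPVT-4 and Matrix Reasoning at the post-consent research screening that is already planned.
2. List the tests in 8.3.2 and add them as a row under Screening in section 19.
3. State in 8.3.2 that equipment is sent after eligibility on the screening tests is confirmed. The tolerability test needs the device and necessarily comes later.
4. Define the 30, and the denominator for percent compliance, as participants who pass screening, so that test failures do not use a place. Section 8.1 calls people who cannot tolerate the baseline stimulation test screen failures, so say explicitly whether the definition covers them. Report the number who signed and the number who failed screening, so that the losses remain visible.
5. Reconcile the WRAT/PPVT limit and its direction across Inclusion Criteria, Vulnerable Subjects and Capacity to Consent, and check the direction of criterion 4 at the same time. Which limit applies is for the investigators to decide.

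The cost is protocol and schedule wording. No test or visit is added. Shipment may be delayed by a few days, and more than 30 people may have to sign consent to reach 30 who pass screening.

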5.2 Duration of Study Participation

Study participation will last approximately 1 month and will include:

- Remote consent (20 minutes), with participant provided as much time as they need to review consent form. Once consented, participant will be scheduled for telehealth research screening. The screening will be scheduled based on participant and study/physician availability, which can occur on the same day as consent and anticipated to be within one week of consent.
- Baseline speech and language assessment & tDCS Session 1 (approximately 3 hours: 20 minutes to orient to device, 1.5 hour assessments, 30 minute tDCS session, 15 additional minutes of word naming practice).
- tDCS treatment sessions (20 x 30 min session over 4 weeks)
- tDCS Session 20 & Treatment-end (2 hours)

5.3 Total Number of Participants and Sites

Recruitment will end when approximately 30 participants are enrolled (sign consent) through NYU Langone Health, Department of Neurology.

5.4 Participant Withdrawal or Termination

5.4.1 Reasons for Withdrawal or Termination

Participants are free to withdraw from participation in the study at any time upon request. An investigator may terminate participation in the study if:

- Any clinical adverse event (AE), laboratory abnormality, or other medical condition or situation occurs such that continued participation in the study would not be in the best interest of the participant
- The participant meets an exclusion criterion (either newly developed or not previously recognized) that precludes further study participation.

5.4.2 Handling of Participant Withdrawals or Termination

If a participant wishes to withdraw from the study they may do so at any point without adverse effect on their standard-of-care treatment. Participants will be provided with study team e-mail and contact number and can withdraw at any time.

